#### 9.2 Primary PK Analyses

The primary PK analyses describe the concentrations of MIV-150 in the following matrices: 1) blood plasma (BP), 2) rectal fluid (RF), and 3) rectal mucosal tissue homogenates (RT) during each of three sequential dose/volumes of 4mL, 16mL, and 32mL.

As BP samples are collected among all participants at seven time points and RF and RT samples are collected among three participants at each time point up to 24 hours and among four participants at 48 hours for each dose/volume, there are differences between how the concentration data for these matrices will be analyzed and summarized.

In general, due to the small number of concentrations available at sampling time points, a log transformation of the concentrations will be considered if the data suggest strong skewness. In this case, figures and tables will report medians with 95% C.I. at each sampling time point and figures will be presented on a semi-logarithmic scale (y-axis: logarithmic concentration; x-axis: linear time (h)). If no log transformation of concentration is needed, then figures and tables will report the mean (with 95% confidence interval based on a Student's t-distribution approximation) at each sampling time point and figures will be presented on a linear scale.

#### Blood Plasma Concentrations

For blood plasma, MIV-150 concentrations can be plotted over time for each individual participant and PK parameters (defined below) may be calculated for each participant and then summarized across all participants.

Displays of blood plasma concentration data include:

- Tables summarizing the distribution of concentrations at each sampling time point for each dose/volume (3 tables, or 1 table with a column for each dose/volume).
- Plots of individual participant concentration-time data presented in a panel for each dose/volume (3 panels of plots (1 panel for each dose/volume)).

- Individual participant concentration-time data will also be overlaid on a single plot for each dose/volume (3 plots).
- Plots of mean/median concentration at each time point (with 95% C.I.) for each dose/volume (3 plots, or 1 panel with 3 plots (1 for each dose/volume)).
- Listings of individual participant PK parameters for each dose/volume (3 listings).
- Tables summarizing the distributions of PK parameters across all participants for each dose/volume (3 tables).

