7.4 Follow-up Visits

7.4.1 Dosing – Visits 3, 5, and 7

The first dosing on Visit 3 should occur approximately 14 days after the Enrollment Visit.

After a two-to-six-week washout period (to accommodate scheduling around the menstrual cycles of female participants) following each dosing visit, participants will return to the clinic for assessment. If no adverse events (AEs) that preclude continuation to the next dose are identified (based on product hold criteria in Section 9 and discretion of the loR/designee), participants will receive the next scheduled dose of the study gel. Please see the SSP Manual for additional information.

All participants will undergo PK and PD assessments within 24 hours after each gel administration. Participants will be randomized 1:1:1:1 to one of the following 4 time frames to provide samples of rectal tissue, rectal fluid, vaginal fluid (if applicable), and effluent from rectal lavage: 0.5-1 hour, 1.5-3 hours, 3.5-5 hours, and 24 hours following PC-1005 gel application. This time frame will remain consistent across gel volumes.. Procedures for the day of dosing are listed in

Table 13 below.

Table 13: Dosing Procedures

able 1	3: Dosing Procedures	ing Dunnadanan Maita O. F. and 7	
	Dosing Procedures – Visits 3 , 5, and 7 Component Procedures		
	Component		
Admi	inistrative and Regulatory	Noview aparte locater information	
		Provide reimbursement	
		Schedule next visit/contact	
Е	Behavioral/Counseling	Protocol counseling	
		Behavioral assessment	
		Review/update medical history	
		 Perform targeted physical examination* 	
		Perform male genital examination*	
		Perform pelvic examination*	
	Clinical	Perform rectal examination	
		Review/update concomitant medications	
		Treat or prescribe treatment for RTI/UTI, or STIs*	
		Disclose available test results	
		Record/update AEs	
	Pharyngeal	NAAT for GC/CT*	
		NAAT for GC/CT*	
	Urine	Urine dipstick/culture*	
		Qualitative hCG ♀	
		CBC with differential and platelets*	
حَ	Blood	Chemistries (Creatinine only)	
ato	2.000	Syphilis serology*	
Laboratory		Blood for PK ■ Blood fo	
La	Pelvic	Vaginal fluid for PK△♀	
		NAAT for GC/CT/TV*♀	
		Rectal enema effluent for PD prior to biopsy collection ∴	
	Anorectal	Rectal fluid for PK and PD	
	Allolottal	Rectal tissue for PK, PD, histology, and archive	
		HSV 1/2 detection*	
		NAAT for GC/CT*	
S	tudy Product/Supplies	Administration of study product	
		Offer condoms	

^{*} If indicated. ♀Female participants.

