10.5 Randomization Procedures

There will be no randomization to dose/volume of PC-1005 in this open-label, sequential dose/volume escalation trial. However, upon enrollment a participant will be assigned to a randomly selected sequence of pharmacokinetic sampling times for administration of flexible sigmoidoscopy biopsy procedures.

Each participant will have a total of 5 flexible sigmoidoscopies:

- at baseline (1 set of biopsies);
- within 24 hours of each of the three dose/volume gel applications (one of the following randomly selected times: 0.5-1 hour, 1.5-3 hours, 3.5-5 hours, or 24 hours after gel administration for each dose/volume of gel) (total of 3 sets of biopsies), and
- 48 hours after one of the three dose/volume gel applications (to be determined at random) (1 set of biopsies).

The sampling schedule for a participant will be preassigned at the enrollment visit.

The determination of the sample schedule will achieve the following characteristics:

- All 12 participants will have flexible sigmoidoscopy at enrollment.
- For the 4 mL, 16 mL, and 32 mL dose/volumes, participants will be randomly assigned 1:1:1:1 to one of the following 4 time frames to provide samples of rectal tissue, rectal fluid, vaginal fluid (if applicable), and effluent from rectal lavage: 0.5-1 hour, 1.5-3 hours, 3.5-5 hours, and 24 hours following PC-1005 gel application.
- There will be 3 sets of biopsies available at each time frame (0.5-1 hour, 1.5-3 hours, 3.5-5 hours, and 24 hours following PC-1005 gel application) for each dose/volume (4 mL, 16 mL, and 32 mL).
- Across the three dose/volumes (4 mL, 16 mL, and 32 mL), participants will be randomly assigned 1:1:1 to provide samples of blood, rectal tissue, rectal fluid, vaginal fluid (if applicable), and effluent from rectal lavage48 hours following PC-1005 gel application for one of the three dose/volumes.
- There will be 4 sets of biopsies available at 48 hours following PC-1005 gel application for each dose/volume (4 mL, 16 mL, and 32 mL).
- Randomizations will be stratified by gender so as to incorporate 1-2 participants of each gender at each of four time frames between 0.5 and 24 hours, and to incorporate 2 participants of each gender at 48 hours for each dose/volume.

The randomization scheme will be generated and maintained by the MTN SDMC.

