13.4 Risk Benefit Statement

13.4.1 Risks

It is not expected that this trial will expose human subjects to unreasonable risk.

Vaginal Fluid Collection

Collection of vaginal fluid may cause discomfort or pressure in the vagina or genital area.

Phlebotomy and IV Cannula Placement

Phlebotomy may lead to discomfort, feelings of dizziness or faintness, and/or bruising, swelling, having a blood clot, excessive bleeding, and/or infection.

Pharyngeal Swab

Pharyngeal (throat) swab collection often causes a momentary gagging reflex.

Rectal Enema

An enema is a standard procedure that may be used prior to insertion of a flexible sigmoidoscope since fecal matter can obscure the test. The main risk from having an enema is temporary discomfort. A hollow tube about the thickness of a pencil will be used to put approximately 120 mL of normal saline 0.9% into the rectum and flush it out again (a larger volume may be required if the initial volume does not produce results), along with any stool that is there. Some air may be pumped into the rectum as well, causing flatulence. There is a risk of a bloated/cramping feeling. The tube is small, but it might cause some anal or rectal discomfort if the subject has any hemorrhoids or other painful conditions.

Anoscopy

Insertion of a lubricated anoscope will likely cause some discomfort.

Flexible Sigmoidoscopy and Rectal Biopsy Collection

Flexible sigmoidoscopy is a commonly practiced endoscopic medical procedure and will not involve any increased risk over usual sigmoidoscopy performed for clinical indications. There is a low risk of infection, mild rectal irritation, low blood pressure, and feeling a sudden urge to defecate during or after the flexible sigmoidoscopy procedure. There is a very low risk of an intestinal tear during the flexible sigmoidoscopy procedure.

There is a risk of limited rectal bleeding 1-2 days after flexible sigmoidoscopy, associated with collection of biopsy samples. The rate of perforation of a hollow viscus following endoscopic biopsy occurs less than 88 out of every 100,000 times.⁴⁹ A recent retrospective analysis of approximately 1,000 research flexible sigmoidoscopies (including collection of rectal biopsies) conducted at the University of Pittsburgh demonstrated an overall adverse event rate of 1.6%. The majority of AEs were gastrointestinal in nature and of mild/moderate severity.⁵⁰

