#### 2.3.1 Randomization

There will be no randomization to dose/volume of PC-1005 in this open-label, sequential dose/volume escalation trial. However, upon enrollment a participant will be assigned to a randomly selected sequence of pharmacokinetic sampling times for administration of flexible sigmoidoscopy biopsy procedures. Each participant will have a total of 5 flexible sigmoidoscopies:

- at baseline (1 set of biopsies);
- within 24 hours of each of the three dose/volume gel applications (one of the following randomly selected times: 0.5-1 hour, 1.5-3 hours, 3.5-5 hours, or 24 hours after gel administration for each dose/volume of gel) (total of 3 sets of biopsies), and
- 48 hours after one of the three dose/volume gel applications (to be determined at random) (1 set of biopsies).

The sampling schedule for a participant will be preassigned at the enrollment visit.

The determination of the sample schedule will achieve the following characteristics:

- All 12 participants will have flexible sigmoidoscopy at enrollment.
- For the 4 mL, 16 mL, and 32 mL dose/volumes, participants will be randomly assigned 1:1:1:1 to one of the following 4 time-frames to provide samples of rectal tissue, rectal fluid, vaginal fluid (if applicable), and effluent from rectal lavage: 0.5-1 hour, 1.5-3 hours, 3.5-5 hours, and 24 hours following PC-1005 gel application.

- There will be 3 sets of biopsies available at each time-frame (0.5-1 hour, 1.5-3 hours, 3.5-5 hours, and 24 hours following PC-1005 gel application) for each dose/volume (4 mL, 16 mL, and 32 mL).
- Across the three dose/volumes (4 mL, 16 mL, and 32 mL), participants will be randomly assigned 1:1:1 to provide samples of blood, rectal tissue, rectal fluid, vaginal fluid (if applicable), and effluent from rectal lavage 48 hours following PC- 1005 gel application for one of the three dose/volumes.
- There will be 4 sets of biopsies available at 48 hours following PC-1005 gel application for each dose/volume (4 mL, 16 mL, and 32 mL).
- Randomizations will be stratified by gender so as to incorporate 1-2 participants of each gender at each of four time-frames between 0.5 and 24 hours, and to incorporate 2 participants of each gender at 48 hours for each dose/volume.

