# 2.3.3 Sample Size and Power

The study is designed for a total accrual of twelve (12) participants, which gives sufficient power for the detection of events (adverse events or detection of drug) as described in the protocol. Descriptive safety analyses and pharmacokinetic analyses are planned with no formal statistical testing.

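### Nine of 12 participants have an enema and biopsies 0.5–5 h after each dose while plasma sampling continues, yet the SAP pools all plasma profiles and merges post-lavage 48-h rectal values into one curve, with no display by sampling frame

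*SAP*

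**What the plan says.** Under SAP 2.3.1, "participants will be randomly assigned 1:1:1:1 to one of the following 4 time-frames" after each dose: 0.5–1, 1.5–3, 3.5–5 or 24 h. Protocol Table 13 (section 7.4) lists "Rectal enema effluent for PD prior to biopsy collection" among the procedures tied to that assigned time. Protocol 13.4.1 describes the enema as putting "approximately 120 mL of normal saline 0.9% into the rectum and flush it out again", with more if needed. Protocol 7.10 adds about nine biopsies per post-dose sigmoidoscopy. It counts five sigmoidoscopies per participant: baseline, one within 24 h of each of the three doses, and one at 48 h after a single dose.

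Plasma does not follow the sampling frames. SAP 9.2 states that "BP samples are collected among all participants at seven time points": pre-dose, then 1, 2, 3, 4, 5–6 and 24 h. For plasma, "PK parameters (defined below) may be calculated for each participant and then summarized across all participants", separately for each volume. SAP 3.2 places PK results by actual collection time and sets the randomised timing group aside.

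For rectal fluid (RF) and rectal tissue (RT), SAP 9.2 builds one profile per volume from different participants at different times, including 48 h, and takes PK parameters from its means or medians. SAP 10.2 repeats this for vaginal fluid.

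**The concern.** Systemic and compartmental PK is a primary objective, and Protocol 2.5 states that there are no earlier rectal data for MIV-150. If the enema carries away unabsorbed gel, a plasma profile continued after it describes gel that was partly removed, at a time that differs by frame. Pooling then mixes four conditions in one Cmax, tmax, AUC and half-life, and the planned tables cannot show whether that matters. Protocol 10.7.2 itself allows that lavage may carry drug: it plans to test lavage fluid for anti-HIV activity and relate it to MIV-150 concentration.

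The 48-h values raise a similar problem. The composite rectal curve would join values taken at a participant's first post-dose procedure to values taken after an earlier procedure for the same dose, so the late part of the curve may fall partly because of the sampling.

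**Working it through.** **Allocation counts.** SAP 2.3.3: "The study is designed for a total accrual of twelve (12) participants". Then 12/4 = 3 per frame, which reproduces the SAP's own figure ("There will be 3 sets of biopsies available at each time-frame"). Also 12/3 = 4 at 48 h, which reproduces Protocol 10.5 ("There will be 4 sets of biopsies available at 48 hours following PC-1005 gel application for each dose/volume"). Three frames fall on the dosing day: 3 × 3 = 9 of 12 participants per dose.

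**Enema volume against gel volume.** 120/4 = 30, 120/16 = 7.5 and 120/32 = 3.75 times the dose.

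**Plasma draws after the procedure.** There are six post-dose draws to 24 h per participant, so 12 × 6 = 72 per volume. Taking 5–6 h as 5.5 h:

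| Frame | Draws after the procedure (of 6) |
|---|---|
| 0.5–1 h | 5–6 |
| 1.5–3 h | 3–5 |
| 3.5–5 h | 2–3 |
| 24 h | 0–1 (depends on the order at that visit) |

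Minimum: 3 × (5+3+2+0) = 30. Maximum: 3 × (6+5+3+1) = 45. The count is approximate, because the order of blood draw and procedure at coinciding times is not in the two documents. Plasma drawn at 48 h is additional and always follows a procedure.

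**48-h samples.** The 48-h sigmoidoscopy is additional to the one within 24 h of that dose. So 0 of 4 rectal sets per volume (0 of 12 overall) come from a participant with no earlier enema and biopsies after that dose. The same holds for the vaginal fluid taken with them from female participants.

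**Possible size (illustration).** Assumptions: one compartment, first-order absorption, and a fraction r of unabsorbed gel removed at te = 0.75, 2.25 or 4.25 h. With ke = ln 2 / half-life, ka solves tmax = ln(ka/ke)/(ka − ke). The group AUC ratio to undisturbed is 1 − r·exp(−ka·te), and the 24-h group has ratio 1. Protocol 2.5 gives vaginal median tmax 3–5 h and half-life 3.9–5.5 h. The value of r is not in the documents.

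| tmax, half-life (h) | ka (/h) | Pooled AUC ratio, r = 25% | Pooled AUC ratio, r = 100% |
|---|---|---|---|
| 3, 5.5 | 0.70 | 0.95 | 0.79 |
| 4, 4.8 | 0.40 | 0.92 | 0.67 |
| 5, 5.5 | 0.30 | 0.90 | 0.60 |
| 1, 4.8 (rapid rectal absorption) | 3.26 | 0.99 | 0.98 |

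Worked row (ka 0.40, r = 1): 1 − exp(−0.30) = 0.26, 1 − exp(−0.90) = 0.59, 1 − exp(−1.70) = 0.82. The pooled ratio is (0.26 + 0.59 + 0.82 + 1)/4 = 0.67. Across the vaginal scenarios the pooled sampled Cmax ratio runs from 0.96 to 0.77, and the AUC ratio in the 0.5–1 h group from 0.85 to 0.20.

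**Half-life rule.** SAP 9.2 requires at least three concentrations after Cmax. An undisturbed plasma profile peaking at 4 h has only the 5–6 h and 24 h draws left, unless that participant also has the 48-h visit for that dose. A profile cut short at 1–2 h has enough points. Half-life and extrapolated AUC could therefore come disproportionately from profiles affected by the procedure.

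**The case against.** Several points on the other side stand.

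- **Direction.** A reader might infer that pooling definitely understates exposure. The documents do not support that. They give no removal fraction and no rectal absorption rate, and they do not address whether biopsies or spreading of the gel by saline might raise absorption. The model counts removal only.
- **Safety.** A reader might call this an unsafe bias. Escalation under Protocol 7.4.1 and section 9 rests on adverse events and hold criteria, not on plasma PK. Scaling the vaginal 4 mL Cmax (75–114 pg/mL) eight-fold to 32 mL gives at most 912 pg/mL. Dividing by 0.60 gives about 1.5 ng/mL, some 28-fold below the lowest oral level cited (42 ng/mL). Proportional scaling and carrying vaginal absorption over to the rectum are both assumptions.
- **Rectal half-life.** A reader might suppose that if the earlier lavage removed half the drug, a true 24-h half-life would be reported as 12 h. The SAP's rule cannot use a 24–48 h slope alone, because it needs three points after the peak and takes the first and last of them. From 4.25 to 48 h there would be 43.75/24 + 1 = 2.82 halvings in 43.75 h, or 15.5 h; starting from 2.25 h it is 15.7 h. The one-half is itself unsupported.
- **Rectal fluid.** The enema is placed before biopsy but is not ordered against fluid collection. Calling all 0.5–24 h fluid values lavaged goes too far.
- **Existing displays.** Concentrations are listed per participant, and individual plasma plots and parameter listings are planned. They need not show the frame or procedure time, so they do not cure the pooled primary summaries.
- **Between-volume comparisons.** Protocol 7.4.1 keeps a participant's frame the same at all volumes, which partly protects within-participant comparisons. Protocol 10.5 and SAP 2.3.1 can be read as a new random time per dose. Absolute parameters are affected either way.
- **Precision.** Making the 24-h group the headline would widen the t-based 95% CI half-width from 2.201/√12 = 0.64 SD to 4.303/√3 = 2.48 SD. That argues against replacing the n=12 summary.

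**Conclusion.** The concern holds as a matter of structure. Nine of 12 participants per dose have the enema and biopsies at 0.5–5 h, and about 30–45 of 72 post-dose plasma samples per volume follow the procedure. All four 48-h rectal sets per volume follow an earlier one, and the SAP neither separates nor flags any of this. These counts rest only on the documents' allocation and nominal times.

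The bias itself is not established. Lower apparent plasma exposure than with gel left in place is the likely effect. On the removal-only model the pooled AUC ratio is about 0.95–0.60 for 25–100% removal under vaginal kinetics, and about 0.99–0.98 if rectal tmax is near 1 h, so the effect may be large or negligible. The planned summaries cannot tell which. That justifies changing the analysis displays. It does not show that the trial's design or escalation rule is unsound.

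**What to change.** In SAP 9.2 and 10.2:

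1. Keep the n=12 plasma summary. Add tables and plots of plasma concentrations and PK parameters by randomised rectal-sampling frame, and mark the recorded procedure time on individual profiles.
2. Add a sensitivity summary at each time point using only samples drawn before that participant's enema. By nominal frames this retains at least 9 participants at 1 h, 6 at 2 and 3 h, and 3 at 4 and 5–6 h. At 24 h it retains up to 3, if blood is drawn first.
3. Show full-profile Cmax and AUC for the 24-h group descriptively (n=3), stated to be imprecise.
4. Label 48-h RF, RT and vaginal-fluid values as taken after prior lavage and biopsy. Report composite AUC, ke and half-life with and without them. Without 48 h only four times remain, so under the three-point rule ke and half-life exist only if the composite peak is in the 0.5–1 h frame; the SAP should say so.
5. Reconcile Protocol 7.4.1 with Protocol 10.5 and SAP 2.3.1 on whether a participant's frame is fixed across volumes.

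This needs SAP wording and the recorded enema and biopsy times, with no change to visits or sampling. The cost is extra displays and small numbers in the undisturbed subset.

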#### Rectal Fluid and Rectal Tissue Concentrations

For rectal fluid and rectal tissue, the concentration-time profile will consist of data from different participants at different sampling time points. Individual participant PK parameters will not be calculated for concentration data from rectal fluid and rectal tissue since data were not collected at each time point for each participant.

Displays of rectal fluid and rectal tissue concentration data include:

- For each matrix (RF, RT), tables summarizing the distribution of concentrations at each sampling time point for each dose/volume (3 tables per matrix, or 1 table per matrix with a column for each dose/volume).
- For each matrix (RF, RT), scatter plots of MIV-150 concentration-time data for each dose/volume (3 plots per matrix, or 1 panel per matrix with 3 plots (1 for each dose/volume)).
- For each matrix (RF, RT), plots of mean/median concentration at each time point (with 95% C.I.) for each dose/volume (3 plots per matrix, or 1 panel per matrix with 3 plots (1 for each dose/volume)).
- For each matrix (RF, RT), tables of PK parameters calculated from mean/median concentrations at each sampling time point for each dose/volume (3 tables per matrix).

# The PK parameters are:

Cmax Maximum observed MIV-150 concentration.

Clast Last observed MIV-150 concentration.

tmax Time of occurrence for Cmax

AUC0-t Area under the MIV-150 concentration-time curve to the time of the last measurable

concentration.

AUC0-∞ Area under the MIV-150 concentration-time curve to infinite time. Equal to AUC0-t plus

 $AUC_{t-\infty} = (C_{last} / k_e).$ 

ke Terminal elimination rate constant.

 $t_{1/2}$  Half-life of drug elimination in the terminal phase.

%AUCex Percentage of AUC0-∞ obtained by extrapolation, calculated as [(Clast / ke) / AUC0-∞ \*100]

The time, in hours, to each sample collection time is calculated from the time of dose insertion. The area under the curve (AUC) is calculated for each participant using the trapezoidal method from the time of dose insertion to the time of the last sample collection (AUC $_{0-t}$ ), typically at 24h or 48h.

Concentrations after  $C_{max}$  are used to determine the terminal elimination rate constant ( $k_e$ ) and associated half-life of MIV-150 elimination in the terminal phase ( $t_{1/2}$ ), when at least three such concentration values are available, according to the following formulas:

$$k_e = \ln (C_1/C_2) / (t_2 - t_1)$$
  
 $t_{1/2} = \ln(2) / k_e$ 

where In is the natural logarithm,  $C_1$  is the first MIV-150 concentration value in the elimination phase after  $C_{max}$ ,  $C_2$  is the last MIV-150 concentration in the elimination phase after  $C_{max}$ , and  $t_1$  and  $t_2$  are the time (hours) of the first and last MIV-150 concentration values in the elimination phase after  $C_{max}$ , respectively, as measured from the time of dose insertion.

The area under the plasma MIV-150 concentration-time curve to infinite time (AUC0-∞) is calculated by extrapolating the area of the curve after the last observed plasma MIV-150 concentration ( $C_{last}$ ) by dividing  $C_{last}$  by the terminal elimination rate constant ( $k_e$ ) and adding the result to AUC0-t. The percentage of AUC0-∞ obtained by extrapolation (%AUCex) is calculated as [(AUCt-∞ / AUC0-∞)\*100].

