2.5 Clinical Studies

MIV-150 Oral Formulation Trials

MIV-150 was studied in 4 Phase 1 clinical trials (see Table 8 below) in men using different oral formulations and dose levels by Chiron Corporation. There were no SAEs reported in association with MIV-150 oral administration. None of these 4 studies achieved the target systemic trough concentration of greater than 120 ng/mL considered necessary for antiviral efficacy. 19 In the Chiron clinical development program, MIV-150 was given to over 60 volunteers in these 4 studies using micronized and nanocrystal dispersion (NCD) formulations. MIV-150 was well-tolerated in 2 single and 2 multiple oral dose studies with doses of 200 to 1600 mg per day. Relative bioavailability was greater for the NCD than the micronized suspension. Treatment-emergent clinical events related to study drug were mild and transitory, and consisted of somnolence, fatigue, and anorexia. After administration of NCD, the absorption of MIV-150 was rapid, with C_{max} occurring within 2 hours. After attaining C_{max}, plasma concentrations declined rapidly in an apparent biphasic manner, and 12-hour trough levels were lower than expected. To achieve higher trough levels, 2 controlled-release (CR) formulations of MIV-150 with zero-order (CR01) and first-order (CR02) release kinetics were studied (MIV-102; Table 8). Although there was no significant difference between the 2 formulations, the extent of exposure was up to 17% greater for CR01 than CR02. CR01 was then selected for a multiple dose Phase 1 study (MIV-103, Table 8). Mean trough levels of approximately 48.4 + 29 and 100 + 70 ng/mL were achieved with 800 mg BID and 400 mg TID regimens, respectively. The AUC(0-∞) and Cmax values increased in a less than dose proportional manner over the ascending dose levels in all 4 trials, indicating that absorption is dissolution rate limited. Neither the CR01 nor CR02 formulations provided a superior profile to the parent NCD formulation.

Additional trial details appear below in Table 8 and in the IB.19

Table 8: Summary of Completed Clinical Studies with MIV-150

Study	Study Name	Population (N)	(Oral) Dose	Findings:	Findings:

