# 9. PHARMACOKINETIC ANALYSES

Descriptive statistics will be used to summarize actual PK sample collection times (from dose insertion) for plasma, rectal fluid, rectal tissue, and vaginal fluid samples, and these summaries will be provided by site and overall. Plasma samples are expected to be collected pre-dose and at 1h, 2h, 3h, 4h, 5-6h, and 24h after dose administration. Samples of rectal fluid, rectal tissue, and vaginal fluid (if applicable) are expected to be collected at one of the following time points, 0.5-1h, 1.5-3h, 3.5-5h, or 24h during each dose/volume administration (chosen randomly 1:1:11). These samples are also expected to be collected at 48h after dose administration for one of the three dose/volume levels (4 mL, 16 mL, or 32 mL; chosen randomly 1:1:1).

A table summarizing the number and percentage of plasma, rectal fluid, rectal tissue, and vaginal fluid samples collected outside of the windows of the expected time points will be provided overall and by site. For samples collected outside of the window, a listing of sample collection times along with the amount of time before (-) the window or after (+) the window will be provided. Allowable windows for the collection of plasma, rectal fluid, rectal tissue, and vaginal fluid are detailed in section 5.4.2 and Table 5-1 of the MTN-037 SSP Manual.

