#### 9.1 Methods for Handling Missing and BLOQ Data

Each bioanalytical assay for plasma, rectal fluid, rectal tissue, and vaginal fluid has an assay sensitivity described by a lower limit of quantitation (LLOQ). These LLOQs will be reported for each matrix. Concentration values assayed below the LLOQ, as well as those classified as "Not Detected", are identified as below the limit of quantitation (BLOQ).

In individual participant data listings, actual concentration values below the LLOQ will be displayed, if provided from the lab, along with the LLOQ for the assay. For values identified as BLOQ in the data, a listing will be provided displaying the assay and time point(s) of the BLOQ values.

Pre-dose samples that are BLOQ or missing will be assigned a numerical value of zero for the calculation of area under the concentration-time curve (AUC). Pre-dose samples that are missing will be excluded from the concentration summary calculations at pre-dose. Any anomalous quantifiable concentration values (at or above the LLOQ) observed at pre-dose will be identified in the study report and used for the computation of AUC.

Any other BLOQ concentrations that precede quantifiable samples in the initial portion of the profile or a BLOQ value that occurs between quantifiable data points, especially prior to Cmax, will be evaluated to determine if an assigned concentration of zero makes sense, or if reanalysis or exclusion of the data is warranted. Following Cmax, BLOQ values embedded between two quantifiable data points will be treated as missing when calculating AUC. If BLOQ values occur at the end of the collection interval (after the last quantifiable concentration), these will be treated as missing data. If consecutive BLOQ concentrations are followed by quantifiable concentrations in the terminal portion of the concentration curve, these quantified values will be excluded from the PK analysis by assigning them a value of missing, unless otherwise warranted by the concentration-time profile.

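### SAP 9.2 sets no acceptance rule for the terminal rate constant, so a short plasma tail can put extreme or negative half-life and AUC0-∞ values into the by-volume summaries

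*SAP*

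**What the plan says.** The parameter definitions in SAP 9.2 call ke the terminal elimination rate constant. It is calculated from concentrations after Cmax "when at least three such concentration values are available, according to the following formulas": ke = ln(C1/C2)/(t2 − t1) and half-life = ln(2)/ke. C1 "is the first MIV-150 concentration value in the elimination phase after" Cmax, and C2 "is the last MIV-150 concentration in the elimination phase after" Cmax. AUC0-∞ adds Clast/ke to AUC0-t, and %AUCex is the extrapolated share. The SAP does not define where the elimination phase begins, beyond its following Cmax.

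The schedule in SAP 9 is: "Plasma samples are expected to be collected pre-dose and at 1h, 2h, 3h, 4h, 5-6h, and 24h after dose administration". Under Protocol 10.5, "participants will be randomly assigned 1:1:1 to provide samples of blood, rectal tissue, rectal fluid, vaginal fluid (if applicable") at 48 h, after one of the three volumes only.

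SAP 9.1 adds: "If BLOQ values occur at the end of the collection interval (after the last quantifiable concentration), these will be treated as missing data".

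SAP 9.2 plans listings of plasma parameters for each participant and tables of their distribution for each volume. Protocol 10.7.2 gives no other method for ke.

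**The concern.** The rule counts samples but does not ask whether they can support a slope. Three concentrations within two or three hours satisfy it as well as three spread over a day. Once ke is close to zero or negative, half-life and AUC0-∞ follow it to absurd values. No stated rule keeps these out of a summary of at most about 12 profiles per volume, where one such value can dominate a mean and standard deviation. Requiring three values and then using two also discards information that has already been collected.

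**Working it through.** The plan states no ke, half-life or AUC for this trial, so there is no figure to reproduce. The check applies the SAP's formula to the SAP's own sampling times.

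**Inputs.** Sampling times and the treatment of late BLOQ values are as quoted. From Protocol 2.5 (vaginal gel): half-life 4.82 h in the run-in trial, so ke = ln(2)/4.82 = 0.1438 per h; run-in median Cmax 84.7 pg/mL. Assumptions not in the documents: one-compartment decline, and independent errors with SD s = 0.15 or 0.20 on the log scale (about 15% or 20%). Peak time is taken as given.

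**Which profiles pass.** Number of post-Cmax plasma values:

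| Peak | Data to 24 h | 24 h BLOQ |
|---|---|---|
| 1 h | 5 | 4 |
| 2 h | 4 | 3 |
| 3 h | 3 | 2 (ke withheld) |
| 4 h | 2 (ke withheld) | 1 (ke withheld) |

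A short-span ke therefore needs a BLOQ value at 24 h and a peak at about 2 h or earlier. For a 2 h peak, the fraction of Cmax left at 24 h is 0.5^(22/4.82) = 4.2%, or 3.6 pg/mL from 84.7. BLOQ at 24 h is plausible, but no LLOQ is given.

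**Short-span precision.** For a 2 h peak the usable samples are at 3, 4 and, say, 5.5 h. The span is 2.5/4.82 = 0.52 half-lives (2/4.82 = 0.41 if the last draw is at 5 h). The two-point SE is s√2/(t2 − t1).

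- s = 0.15: SE = 0.15 × 1.414/2.5 = 0.0849; CV of ke = 0.0849/0.1438 = 59%; P(ke ≤ 0) = Φ(−0.1438/0.0849) = 4.5%.
- s = 0.20: SE = 0.1131; CV 79%; P(ke ≤ 0) = 10.2%.
- Last draw at 5 h instead: P(ke ≤ 0) is 8.8% and 15.5%.
- Peak at 1 h (first value 2 h, last 5.5 h): P(ke ≤ 0) is 0.9% and 3.8%.

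**What an accepted profile can report.** Made-up values of 0, 60, 85, 80, 70, 79 pg/mL at 0-5 h, with 24 h BLOQ:

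- AUC0-t = 30 + 72.5 + 82.5 + 75 + 74.5 = 334.5.
- ke = ln(80/79)/2 = 0.00629, so half-life is 110 h.
- AUC0-∞ = 334.5 + 12,560.8 = 12,895, and %AUCex is 97.4%.

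If the last value is 81, half-life is −112 h and AUC0-∞ is −12,705.

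**Is the two-point formula the cause?** Least squares has slope variance s²/Sxx, where Sxx is the sum of squared deviations of the sampling times from their mean. The ratio to the two-point variance is (t2 − t1)²/(2·Sxx).

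| Post-Cmax times (h) | Ratio, all points |
|---|---|
| 3, 4, 5.5 | 6.25/6.33 = 0.99 |
| 3, 4, 5 | 4/4 = 1.00 |
| 4, 5.5, 24 | 400/496.3 = 0.81 |
| 3, 4, 5.5, 24 | 441/596.4 = 0.74 |
| 2, 3, 4, 5.5, 24 | 484/677.6 = 0.71 |
| 4, 5.5, 24, 48 | 1936/2531.4 = 0.76 |
| 3, 4, 5.5, 24, 48 | 2025/3014.4 = 0.67 |
| 2, 3, 4, 5.5, 24, 48 | 2116/3384.4 = 0.63 |
| 5.5, 24, 48 | 1806.3/1816.3 = 0.99 |

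At 3, 4 and 5.5 h with s = 0.15, regression moves the CV of ke from 59.0% to 58.6% and P(ke ≤ 0) from 4.5% to 4.4%. About 24% of half-lives are wrong by more than two-fold under either method. Both made-up profiles give the same ke by regression, because their three points are equally spaced.

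With data to 24 or 48 h and a peak by 3 h, regression on all points removes 19-37% of the variance of ke. A fit to the last three points alone gives ratios of 0.81-0.98 to 24 h, and is noisier than the SAP's formula to 48 h (1.07-1.16).

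**The case against.** The best defence is that the failure is narrow and the consequence modest. It needs both a BLOQ 24 h sample and an early peak. The vaginal data in Protocol 2.5 put median tmax at 3.92 h in the run-in trial (range 1.97-6.00) and at 3-5 h in the main trial (range 2-12), so a peak at 2 h is at the edge of what is cited. The three-value rule already withholds ke for a 3 h peak with 24 h BLOQ. When 24 h is quantifiable, precision is good: at 4, 5.5 and 24 h with 15% error the CV of ke is 7.4% by the formula and 6.6% by regression. The primary PK endpoint is the concentrations. The analyses are descriptive, and individual plots, listings, medians and %AUCex would let a reader spot an aberrant profile.

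All of this stands as a limit on size. It does not supply the missing rule: %AUCex carries no threshold, and a visible bad value still enters the mean.

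A reader might also infer that the formula makes half-life depend on who was randomised to the 48 h draw, and that regression would cure this. It would not. In an invented biphasic example (half-lives 2 h and 12 h, slow fraction 20%, first post-Cmax value at 3 h), the formula gives 6.6 h with data to 24 h and 8.7 h to 48 h. Regression on the last three points gives 7.3 h and 9.7 h. The dependence comes from unequal follow-up. The evidence for two phases is also indirect: the statement that "plasma concentrations declined rapidly in an apparent biphasic manner" describes oral dosing, and the vaginal gel summaries report no such pattern. Nor does the SAP compel C1 to be the sample nearest absorption; it leaves the start of the elimination phase undefined.

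**Conclusion.** The point holds in limited form. As written, SAP 9.2 can accept a plasma profile whose ke rests on about half a half-life of follow-up, and can carry an extreme or negative half-life and AUC0-∞ into the by-volume summaries. For a 2 h peak, a last draw at 5.5 h and 24 h BLOQ, about 4-10% of ke values would be negative under 15-20% error. That figure rests on an assumed error size, mono-exponential decline and a half-life borrowed from vaginal dosing.

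The tempting stronger reading is that the two-point formula itself produces the meaningless half-lives. The arithmetic does not support it: in the short-span case regression does almost no better. The absence of acceptance criteria is the main cause. The unused middle samples are a separate, smaller loss of efficiency that appears when data run to 24 or 48 h.

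How often the failure would occur cannot be judged from these documents. The primary concentration endpoint is not affected.

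**What to change.** In SAP 9.2:

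- Define ke as minus the least-squares slope of ln(concentration) on actual time, using at least three quantifiable post-Cmax samples chosen by one pre-stated rule: for example all post-Cmax points, or the best adjusted R² over the last three or more.
- Report ke, half-life and AUC0-∞ only if ke > 0 and the samples span a pre-stated minimum number of estimated half-lives (two, for example). Otherwise list the profile as not estimable.
- Report AUC0-∞ only below a pre-stated %AUCex limit.
- Give the number of evaluable profiles per volume, and mark whether each ends at 24 h or 48 h, since regression does not remove that dependence.

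The particular limits are conventions for the team to choose; the documents supply none. The cost is a paragraph of SAP text and routine programming, with no new data. The downside is that some profiles will be not estimable. At a 4.82 h half-life, two half-lives is 9.6 h, so a plasma profile with nothing quantifiable after 5-6 h would normally drop out of these three parameters. Its concentrations, Cmax, tmax and AUC0-t would still be reported.
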